**HEMODYNAMIC AND CEREBRAL EFFECT OF GENERAL ANESTHESIA PLUS BLOCK
INTERESCALENIC vs SEDATION PLUS BLOCK INTERESCALENIC: THE RECOGNISED
RANDOMIZED CONTROLLED TRIAL**

[name]

Advisor: [name]. [name]

São Paulo

06/29/2022

Abstract:

Recently, there has been an increase in the popularity of minimally invasive surgical techniques, including arthroscopic surgeries for shoulder procedures. Interscalene block is currently the gold standard technique for these surgeries, combined or not with general anesthesia. The last, when used in patients positioned in a beach chair can lead to serious hemodynamic and cerebral changes in the patients. Continuous non-invasive monitoring of the patient's cardiac output can provide data for better hemodynamics management compared to standard monitoring. Therefore, the aim of the study is to compare hemodynamic changes (cardiac output, blood pressure, heart rate, oxygen saturation) and intraoperative cerebral oxygenation using peripheral cerebral saturation monitoring with continuous measurement of cardiac output or standard hemodynamic between two anesthetic techniques for shoulder surgery: interscalene block with sedation versus interscalene block with general anesthesia. The groups will be evaluated as follows: group 1 general anesthesia plus interscalene brachial plexus block and group 2 sedation plus interscalene brachial plexus block. Additionally, each group will be subdivided into two more groups, one with continuous hemodynamic monitoring and the other with standard hemodynamic monitoring, that is, a total of 4 groups in the study. The analyzed variables will include gender, age, ASA, medications in use, comorbidities. Furthermore, duration of procedure and in the anesthetic recovery room, blood pressure, heart rate, cardiac output, peripheral oxygen saturation, cerebral oxygen saturation, BIS value, cardiac index, etCO₂ will be evaluated. Besides, length of hospital stay, delirium, behavioral status and postoperative complication will also be assessed.

Keywords: Orthopedic surgery; General anesthesia; Nervous Blockage; Deep Sedation; Hemodynamic monitoring, cerebral oxygen saturation

1. INTRODUCTION

Recently, there has been an increase in the popularity of minimally invasive surgical techniques, including arthroscopic surgeries, especially those performed on an outpatient basis (1). Arthroscopic orthopedic surgeries were initially proposed for the knee. In 1931, Burman et al performed the first shoulder arthroscopic orthopedic surgeries in a cadaver. Since then, arthroscopic shoulder surgery has been increasingly improved. The indication for shoulder arthroscopy can be both for therapeutic and diagnostic procedures, such as hemiarthroplasty, total shoulder arthroplasty, subacromial decompression, rotator cuff injuries, shoulder instability, degenerative diseases of the acromioclavicular and glenohumeral joint, adhesive capsulitis, biceps pathologies and labrum, infection, among others (2); (3).

Shoulder surgeries can be performed in lateral decubitus, semi lateral decubitus, beach chair and semi beach chair position (1);(3);(4). The lateral decubitus position was the first position described for performing orthopedic shoulder surgery. The patient is set up in lateral decubitus with the arm pulled 35° to 70° in abduction and 15° in forward flexion. The traction rope is attached to a rope and pulley system (1). This positioning made the procedure difficult, as it makes it difficult to view the lower third of the shoulder joint. In 1985, Gross and Fitzgibbons modified the lateral position 30 to 40° posteriorly, leaving the glenohumeral joint with an axial axis parallel to the floor. A traction is performed at the midpoint of the humerus, perpendicular along the axial axis with slight abduction of the arm, with the arm being held by a rod placed at the bottom of the table (5). That change in position facilitated the visualization of structures and instrumentation, became it more efficient. Even with the modification of the lateral position, there are some disadvantages, such as non-anatomical position, the arm must be rotated for more anterior access, if conversion to open surgery is needed, it must be repositioned, patients do not tolerate only regional anesthesia, traction can cause neurovascular injury such as peroneal nerve and brachial plexus injury with an incidence of 10 to 30%, decreased limb perfusion. In addition, there is an increased risk of injury to the axillary and musculocutaneous nerve with the use of the portal in the antero-inferior region. Despite this, there are some advantages over the lateral decubitus position, as traction increases the space in the joint, and in the subacromial region and accentuates the labrum, the patient's head and operating table are not in the posterior and superior path of the shoulder and has less risk of hypotension/bradycardia, having better cerebral perfusion (4);(6).

The beach chair position was suggested in 1988 by Skybar to avoid complications from the lateral decubitus position. The patient is set up in a sitting position with at least 60°, the patient's shoulder is brought slightly off the table with a sheet under the scapula (3). This position makes it possible to prevent neurological complications, such as neuropathies of the brachial plexus, peroneal nerve, axillary and musculocutaneous nerve, and facilitates the visualization of structures. In addition to these advantages, a more anatomical position can also be inferred, facilitates the examination under anesthesia, hanging arm does not hinder the visualization of the anterior portals, does not need repositioning for conversion to open surgery, can be performed only with regional anesthesia, arm mobility during the surgery. There are some disadvantages, such as increased risk of hypotension and bradycardia with cardiovascular and neurological complications, dark band in the visualization of the subacromial space, fluid under the camera making visualization difficult, increased risk of air embolism and expensive surgical table equipment (3);(4);(6). The beach semi-deck position is a position that reduces the chair angle to 30° to try to reduce hemodynamic complications (7). These changes can be enhanced by the anesthetic technique used, such as general anesthesia, especially in elderly and hypertensive patients, and when controlled hypotension methods are used for better visualization of the surgical field (8). No technique is totally risk free; however, the most used technique today is the beach chair position. There are several hemodynamic monitoring techniques for intraoperative evaluation, such as invasive and non-invasive monitoring. Non-invasive hemodynamic monitoring can be the standard (heart rate and blood pressure) or continuous monitoring of cardiac output plus heart rate and blood pressure. In addition, there is also monitoring of cerebral oxygenation continuously. The use of continuous monitoring of cardiac output and monitoring of cerebral oxygenation can minimize complications in patients undergoing surgery in a beach chair position through early detection of cerebral hypoperfusion and hypotension, thus, complications are early reversed (9);(10);(11);(12);(13).

Anesthesia for shoulder orthopedic surgery can be performed with general anesthesia, interscalene brachial plexus block associated with sedation, and general anesthesia associated with interscalene brachial plexus block. The anesthetic technique chosen will depend on the type of shoulder surgery and patient acceptance. Prolonged surgeries, analgesia complementation and patient failure or refusal of regional anesthesia is indicative of general anesthesia use (14);(15). General anesthesia is associated with a decreased in the sympathetic effect, systemic vascular resistance and, consequently, a

decreased in mean arterial pressure, cardiac output, and cerebral blood flow. Interscalene block is the gold standard technique and most often used for shoulder procedures, this technique favors shorter anesthetic recovery time, less postoperative pain, use of narcotics and incidence of nausea/vomiting (16);(17);(18).

Literature (18);(19);(20) has shown superiority of sedation in conjunction with interscalene brachial plexus block in relation to general anesthesia (GA) and interscalene brachial plexus block, however there are few studies comparing cerebral and hemodynamic behavior and the type of anesthesia.

The prospective study by Gillespie et al (21) with 52 patients undergoing interscalene blockade associated with laryngeal masking or orotracheal intubation demonstrated at least one hypotension event in all patients. In addition, three patients had ischemic events. However, the patients did not show changes in the mini mental state examination. The study by Soeding et al (22) evaluated 40 patients, who were divided into two groups: interscalene block with sedation versus interscalene block with laryngeal mask in spontaneous ventilation. Cerebral blood flow, MAP (mean arterial pressure) and HR (heart rate) were evaluated. The group using a laryngeal mask had a significant decrease of approximately 32% in MAP. Regarding cerebral blood flow, there was no significant difference.

These data were similar to those found in the study by Agirre et al (23) , which prospectively evaluated 52 patients undergoing orotracheal intubation with interscalene block. There was a decrease in MAP both in patients who had ischemic events and patients who did not have ischemic events. Regarding neurobehavioral tests, there was no significant difference. The prospective study by Vincent et al (24) evaluated 140 patients with interscalene blockade associated with controlled target sedation and detected an incidence of hypotension/bradycardia of 5.7% and a lower incidence of the Bezold-Jarisch reflex. The study by Ozzyebek et al 2010 (19) evaluated the use of interscalene blockade with sedation versus interscalene blockade and general anesthesia. Intraoperatively, MAP, heart rate, oxygen saturation and pain score were evaluated using the visual analogue pain scale. A significant decrease in mean arterial pressure was detected when positioned in a beach chair in the general anesthesia group, not requiring the use of ephedrine. Regarding the pain score, it was similar between groups.

Meidert et al 2017 (25) compared the use of continuous monitoring of cardiac output with standard monitoring in orthopedic surgeries and observed a significantly lower MAP and SBP (systolic blood pressure) in the group that used standard monitoring

compared to the group that used continuous non-invasive monitoring. The use of a beach chair position significantly decreases brain saturation in approximately 20% and it was correlated with the level of etCO₂ as demonstrated in the study by Moerman et al 2012 (26) .

Therefore, there are few studies comparing the perioperative hemodynamic and neurological effects of these two techniques. There is no randomized, controlled study in the literature evaluating perioperative hemodynamic effects and neurological changes through the use of standard and continuous monitoring of cardiac output between these two techniques. So, the aim of the study is to compare intraoperative hemodynamic changes and cerebral oxygenation using peripheral and hemodynamic cerebral saturation monitoring with continuous measurement of cardiac output or standard hemodynamics between two anesthetic techniques for shoulder surgery: interscalene block with sedation versus interscalene block with general anesthesia.

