2. OBJECTIVES

2.1. General:

Compare intraoperative hemodynamic changes (cardiac output, blood pressure, heart rate, oxygen saturation) and cerebral oxygenation using peripheral cerebral saturation monitoring and continuous hemodynamic measurement of cardiac output or standard hemodynamics monitoring between two anesthetic techniques for shoulder surgery: interscalene block with sedation versus interscalene block with general anesthesia.

2.2. Specifics:

- Compare changes in cerebral tissue saturation between groups;
- Assess delirium and behavioral changes;
- Verify the superiority of continuous hemodynamic non-invasive monitoring of cardiac output compared to standard hemodynamic monitoring (only heart rate and blood pressure);
- Verify the relationship between standard hemodynamic monitoring (only heart rate and blood pressure) and continuous hemodynamic monitoring of cardiac output plus heart rate and blood pressure and the use of vasopressors, blood transfusion, infused volume;
- Evaluate complications of the anesthetic blockade technique with sedation over the blockade technique and general anesthesia;
- Assess postoperative pain, length of stay post anesthetic recovery and length of hospital stay between groups;

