3.10. Data collect

After receiving an explanation about the procedures to be performed and signing the consent form, patients will be allocated into 4 groups as explained above using a table of random numbers. Data collected will be age, weight, height, race, gender, ASA, comorbidities, medications in use. During the surgical procedure, the analyzed data will be medications, infusion volume, blood components, vasopressor, anesthetic and surgical complications, anesthesia and surgery time.

In addition, systolic, diastolic and mean blood pressure, heart rate, cerebral O₂ saturation, peripheral O₂ saturation, axillary temperature, BIS value, cardiac index (in patients who will use clear sight) and et CO₂ (in patients who will be intubated) every 5 min intraoperatively and during post-anesthetic recovery (PAR) (27).

Postoperatively, the data analyzed will be: anesthetic recovery time, hospital stay, need to be referred to the intensive care unit (ICU), length of stay in the ICU and if the patient died. In addition, the visual numerical pain scale and the descriptive verbal pain scale will also be evaluated in the PVR and 24 hours after the procedure (28).

Sedation assessment will be performed using the intraoperative RASS scale for patients who are allocated to the sedation + interscalene brachial plexus block group and postoperatively for all groups. The values of the RASS scale are shown in table 1. The Confusion Management Method in the ICU (CAM-ICU) scale will be used to assess delirium, the table with the parameters used will be shown in figure 5 (29);(30).

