3.13. Data analysis

Categorical variables will be presented as absolute and relative frequencies.

Quantitative variables will be presented as mean and standard deviation or as median and interquartile range when appropriate. We will use the Kolmogorov-Smirnov test to assess the distribution pattern of continuous numerical variables.

Comparisons between general anesthesia + block and block + sedation will be performed, as well as comparisons between standard and continuous monitoring. Proportions will be compared using the Chi-square test or Fisher's exact test, if the assumptions for using the Chi-square are violated. Quantitative variables will be compared using the Mann-Whitney test or irregularly distributed Anova when appropriate.

Variables with repeated measurements will be analyzed by linear general multiple model (GLM) with Bonferroni correction for P values.

The association between explanatory variables and response will be evaluated using logistic regression models. Variables selected in the bivariate analyzes ($p<0.05$) and those considered clinically relevant will be submitted to multiple logistic regression analyses. Variables with substantial collinearity will be excluded. The result of logistic regression analyzes will be expressed as odds ratios and respective 95% confidence intervals.

All significance probabilities (P values) presented will be two-tailed. P values will be considered statistically significant when less than 0.05. *The Statistical Package for Social Sciences* software version 26.0 (SPSS Inc.®; Chicago, IL, USA) will be used to perform the analyses.

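### Planned procedure type is not recorded, stratified on or used in the quantitative comparisons, which may cost precision for pain and length of stay

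*Combined protocol and SAP*

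**What the plan says.** Section 1 describes how technique is usually chosen: "The anesthetic technique chosen will depend on the type of shoulder surgery and patient acceptance". It adds that "Prolonged surgeries, analgesia complementation and patient failure or refusal of regional anesthesia is indicative of general anesthesia use". The same section lists widely differing indications for shoulder arthroscopy, among them "subacromial decompression, rotator cuff injuries, shoulder instability, degenerative diseases of the acromioclavicular and glenohumeral joint".

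Sections 3.4 and 3.5 admit adults having any arthroscopic shoulder surgery in the beach chair position. On procedural grounds they exclude only emergency cases and surgery on both shoulders.

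One specific objective in section 2.2 is: "Assess postoperative pain, length of stay post anesthetic recovery and length of hospital stay between groups". For baseline, section 3.10 states: "Data collected will be age, weight, height, race, gender, ASA, comorbidities, medications in use". The intraoperative list ends with "anesthetic and surgical complications, anesthesia and surgery time". Neither that section nor the abstract lists the procedure, planned or performed.

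Section 3.12 specifies blocks of 8 and names no stratification factor. Section 3.13 says: "Quantitative variables will be compared using the Mann-Whitney test or irregularly distributed Anova when appropriate". It sends repeated measurements to a general linear model (GLM) and names no covariates for it. Covariates appear only in the logistic regression, where they are chosen by bivariate p<0.05 or by clinical relevance, and none is named.

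**The concern.** Case mix is open, and the protocol's own background links long operations and the need for extra analgesia to the type of anesthesia. It is therefore plausible, though the documents do not state it, that a short decompression and a long repair differ in pain, recovery time and stay. If they do, that variation goes into the error term of every unadjusted comparison of those outcomes. With 25 patients per group, case mix can also differ noticeably by chance. Because the procedure is not in the dataset as specified, the report could not show the mix by group, adjust for it, or tell readers which operations the results cover.

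**Working it through.** **The plan's own figure.** Section 3.6 uses a MAP difference of 12 mmHg, SDs of 10 and 15, alpha 0.025 and power 80%.
- Normal approximation, two-sided: n = (2.241 + 0.842)² × (10² + 15²) / 12² = 9.505 × 325 / 144 = 21.5, so 22 per group and 88 in total.
- With the noncentral t distribution, n is 23 per group, and 23 × 4 = 92, as stated. The final 100 gives 25 per group, or 50 v 50 on each factor.
- Procedure type plays no part in this calculation, so the point leaves the 92 and the 100 unchanged.

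**Which analysis each outcome falls under.** Recovery stay, hospital stay and infused volume are single values, so section 3.13 sends them to Mann-Whitney or ANOVA. Pain is scored in recovery and at 24 hours, and MAP is taken every 5 minutes. Both plausibly go to the repeated-measures GLM.

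**Precision.** The documents give no R² (share of outcome variance explained by procedure class), so a range is assumed. The difference of 0.5 SD and the two-sided 0.05 level are also assumptions for illustration.
- SE of a 50 v 50 difference in SD units: √(2/50) = 0.20. Unadjusted: 0.5/0.20 = 2.5, and power = Φ(2.5 − 1.96) = 70.5%.
- Adjusted: power = Φ(2.5/√(1 − R²) − 1.96). At R² of 5%, 10%, 20% and 30% this gives 72.7%, 75.0%, 79.8% and 84.8%.
- The SE falls to 0.975, 0.949, 0.894 and 0.837 of its unadjusted value. Equivalently, 100 unadjusted patients carry the information of 95, 90, 80 and 70 adjusted ones.

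**The same with rank tests**, by simulation with three equal procedure classes and normal outcomes:
- Mann-Whitney power is about 67% throughout.
- The van Elteren test (Mann-Whitney stratified by class) has power of about 66%, 68%, 71%, 76% and 81% at R² of 0%, 5%, 10%, 20% and 30%. Repeat runs differ by up to about 2 points.
- Under no difference, both tests reject in about 5% of trials.

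**Chance imbalance**, from two independent binomials with an assumed share p of patients having the larger procedure:
- 50 v 50, a difference of 14 points or more: 19% at p = 0.5, 10% at p = 0.2, 3% at p = 0.1.
- 25 v 25, a difference of 20 points or more: 20% at p = 0.5, 11% at p = 0.2, 3% at p = 0.1.
- Shift in an unadjusted 50 v 50 difference = imbalance × procedure effect. An imbalance of 10 to 20 points with an assumed effect of 0.5 to 1.0 SD gives 0.05 to 0.20 SD, which is 0.25 to 1.0 SE after division by 0.20.

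**The case against.** The introduction's statement is background on how clinicians choose a technique. It names patient acceptance as well as type of surgery, and here technique is allocated at random. A reader might infer that procedure type confounds the technique comparison. The documents do not support that: allocation does not depend on procedure, chance imbalance is not bias, and the unadjusted test already allows for it within its 5% error rate. This part of the objection stands in full.

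A reader might also infer that an imbalance would be invisible. That goes too far. Surgery and anesthesia time are recorded and would hint at a gross excess of long operations in one group, and the hospitals could probably retrieve the procedure later. Surgery time still cannot serve as a baseline covariate, because it follows allocation and may itself be affected by technique or monitoring.

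The size of the gain rests on an R² that the documents do not give. Up to about 5% there is almost no gain, and at 0% there is a small loss. The imbalance figures are largest at p = 0.5 and fall quickly for rarer procedures. The outcomes most concerned are secondary ones, for which the plan claims no power. Finally, age, ASA and hospital are also candidate covariates. Procedure type differs from the first two in that the plan does not collect it at all.

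**Conclusion.** The point holds as one of precision and transparency. Any arthroscopic procedure is eligible, yet planned procedure is not collected, not stratified on and not used in the quantitative comparisons. The logistic regression cannot make up for a variable that is absent from the data. Validity is not in question, and the MAP sample size does not change.

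Under the stated assumptions, stratification gains about 4 points of power at R² of 10% (67% to 71%), 9 at 20% and 14 at 30%. It gains almost nothing at 5% or below. Whether procedure is prognostic to that degree is an assumption. The change is worth making because the cost of being wrong is small and recording the field before allocation is easy.

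**What to change.** - **Section 3.10:** record the planned procedure from the surgical booking, before allocation, in three or four prespecified classes, and tabulate it by group.
- **Section 3.13, single-value outcomes:** compare recovery stay, hospital stay and infused volume with a van Elteren test stratified by procedure class, or with a linear model that has class as a covariate. The linear model can also carry the other factor of the four-group design.
- **Section 3.13, repeated outcomes:** add procedure class as a fixed factor in the GLM for pain and, optionally, for MAP.
- **Section 3.13, exclusion:** state that surgery and anesthesia time will not be used as adjustment variables, because they follow allocation.

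The cost is one extra field, 2 or 3 degrees of freedom in a linear model, and about 1 to 2 points of power with the stratified rank test if procedure type proves irrelevant. Sample size, treatment and clinical rules stay as they are.
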